7.5.2 Urine Pregnancy Testing

A pregnancy test will be done on all female subjects according to Appendix 1.

Female subjects with a positive pregnancy test at V10 will not be offered to enter in the extension study and the PI(s) or designee(s) will inform those subject about the risks associated with smoking during pregnancy. All pregnancies detected during the study must be reported and handled as described in section 8.5.

7.6 Sampling Handling and Storage

All blood samples will be tested in one of the two central laboratories (Appendix 3). The pregnancy tests will be done by the personnel at the study sites.

Detailed procedures for sample collection and handling of samples are described in the laboratory manual. Safety laboratory samples will be destroyed as per the laboratory's standard procedures. For the other samples (except biobanking samples), at least one tube per timepoint and per subject should be kept at least up until the finalization of the bioanalytical reports and the database is locked unless the stability for analysis is exceeded.

The bioanalytical laboratory(ies) are listed in Appendix 2.

7.6.1 Blood Samples

Venous blood samples will be collected by qualified and trained site personnel. Subjects should be in a seated position during blood collection.

The maximal total volume of blood drawn for each subject for the extension study at V16 will be around 80 mL, which includes 13 mL for safety and repeated analysis, 10 mL of blood for long-term storage of the biobanking samples for further analysis of BoExp and clinical risk endpoints (only if additional consent is given at V10) and 9 mL for long-term storage of the biobanking samples for further analysis of transcriptomics and lipidomics (only if additional consent is given at V10) (section 7.6.3).

7.6.2 Urine Samples

Spot urine samples will be used for urine pregnancy test and safety urine analysis for each visit.

24-hour urine collection: the day before the visit, subjects will start collection of his/her 24-hour urine. Subjects will discard their first void in the morning. The collection period will start immediately after. After 24-hours \pm 1h of urine collection, subjects will empty their bladder again in the morning of the visit and this urine will be used as the final portion of the 24-hour urine sample. During the collection period, all urine passed must be collected and put into the sampling container. No urine should be passed into the toilet. The start and the end time of

Confidentiality Statement

Data and information contained in this document are considered to constitute trade secrets and confidential commercial information, and the legal protections provided to such trade secrets and confidential information are hereby claimed under the provisions of applicable law. No part of this document may be publicly disclosed without the written consent of Philip Morris Products S.A.

urine collection will be recorded by the subject and checked by the site staff. The volume of 24-hour urine will be measured by the site staff upon collection of urine containers from the subjects. For assessment of urine BoExp, creatinine, 8-epi-PGF_{2α} and 11-DTX-B₂, albumin, and for sample biobanking, aliquots from the 24-hour urine collection will be taken. In the schedule of events (Appendix 1) for the 24-hour urine collection, the dot corresponds to the day on which the 24-hour urine collection period ends.

The 24-hour urine collection will be collected according to Appendix 1

7.6.3 Long-Term Storage (Biobanking)

The facility at which the samples are stored will follow their procedures for destruction of banked samples if a subject withdraws his/her consent for long-term biobanking.

7.6.3.1 Long-Term Storage of Serum/Plasma or Urine

If a subject gives additional consent during V10 for sample biobanking for further analysis of BoExp and clinical risk endpoints, additional samples of urine from the 24-hour collection and serum/plasma will be collected at V16 as follows:

- Samples will be collected from the 24-hour urine collections that started one day before V16 and ended at V16 (5 tubes of 10 mL each).
- Serum/plasma will be collected at V16 (10 mL of blood draw in total). This is to obtain and store 2X 1 mL of serum and 2X 1 mL of plasma.

If a subject gives additional consent during V10 for sample biobanking of whole blood for further transcriptomics and lipidomics analysis, blood will be collected at V16 as follows:

- Blood will be collected for transcriptomics at V16 (5 mL in total). The 5 mL will be split into two tubes of 2.5 mL of whole blood each.
- Plasma will be collected for lipidomics at V16 (4 mL in total). The 4 mL will be split into two tubes of around 500 µL plasma each.

The blood samples for transcriptomics and lipidomics and the data related to these samples will be anonymized and will be the subject of a separate report. Anonymized data and samples are initially single or double coded where the link between the subjects' identifiers and the unique code(s) is subsequently deleted. This is applicable for the blood/plasma biobanking for transcriptomics and lipidomics only.

The samples intended for sample biobanking will be kept frozen; and will be shipped to a central storage facility according to the laboratory manual. After the final the clinical study report (CSR) is signed, samples of plasma/serum/blood will be stored for a maximum of

Confidentiality Statement

Data and information contained in this document are considered to constitute trade secrets and confidential commercial information, and the legal protections provided to such trade secrets and confidential information are hereby claimed under the provisions of applicable law. No part of this document may be publicly disclosed without the written consent of Philip Morris Products S.A.

5 years and samples of urine will be stored for a maximum of 2 years. The blood biobanking for transcriptomics and lipidomics will be stored for a maximum of 5 years.

7.7 Other Study Procedures

7.7.1 Product Use Diary

The subject will capture the number of THS Tobacco Sticks, CCs (menthol and non-menthol), and other nicotine/tobacco containing products used on a daily basis in a product use diary from enrollment until the check-out of V16 (including during the visits). Subjects were trained by site staff on the use of this diary during the original study. The product use diary was supplied by Sponsor and distributed to the subjects by the study site personnel during the original study. If paper diary is used, the subjects will receive instructions from the site staff on how the diary should be completed.

The site will schedule at each visit the next appointments at site in the electronic diary.

7.7.2 Questionnaires

The subject questionnaires and the visual analog scale (VAS) used in this study will be entered by the subject directly in an electronic diary or on paper copy. If a paper copy is used, the VAS scale must be of 100 mm. All subject reported outcome material will be provided in English or Spanish and instructions will be provided in the subject's local language.

7.7.2.1 Fagerström Test for Nicotine Dependence Questionnaire

Subjects will complete themselves the FTND questionnaire according to Appendix 1 in its revised version [37] irrespective of the time of product use.

The questionnaire consists of six questions. The scores obtained on the test permit the classification of nicotine dependence into three levels: mild (0-3 points), moderate (4-6 points), and severe (7-10 points) [37].

7.7.2.2 Cough Questionnaire

Subjects will complete themselves the respiratory symptom "cough" on a VAS, on three Likert scales, and with an open question irrespective of the time of product use according to Appendix 1.

Subjects will be asked if they have experienced a regular need to cough (*e.g.*, whether they have coughed several times in the previous 24 hours prior to assessment). If the answer is 'yes', subjects will be asked to complete a VAS, 3 Likert scales, and to answer the open question. On the VAS, subjects will assess how bothersome their cough was during the previous 24 hours. The VAS ranges from "not bothering me at all" to "extremely bothersome".

Confidentiality Statement

Data and information contained in this document are considered to constitute trade secrets and confidential commercial information, and the legal protections provided to such trade secrets and confidential information are hereby claimed under the provisions of applicable law. No part of this document may be publicly disclosed without the written consent of Philip Morris Products S.A.

Furthermore, subjects will assess the intensity and frequency of cough and the amount of sputum production during the previous 24 hours on Likert scales.

- The intensity of cough will be assessed on a 5-point Likert scale ranging from 1 to 5, with 1 = very mild – 2 = mild – 3 = moderate – 4 = severe – 5 = very severe.
- The frequency of cough will be assessed on a 5-point Likert scale ranging from 1 to 5, with 1 = rarely – 2 = sometimes – 3 = fairly often – 4 = often – 5 = almost always.
- The amount of sputum production will be assessed on a 4-point Likert scale ranging from 0 to 3, with 0 = no sputum – 1 = a moderate amount of sputum – 2 = a larger amount of sputum – 3 = a very large amount of sputum.

Symptoms or worsening of symptoms documented in the VAS do not need to be documented as additional AEs because the VAS will be analyzed as part of the final report. However, it is at the discretion of the PI(s) or designee(s) to decide whether to document such symptoms as additional AEs. The main source for AE collection will be the face-to-face interview between the subject and study site staff, using open, non-directive questions (section 8.2).

7.7.2.3 Modified Cigarette Evaluation Questionnaire

Subjects will complete themselves the modified cigarette evaluation questionnaire (MCEQ) [38] according to Appendix 1 .

The MCEQ assesses the degree to which subjects experience the reinforcing effects of smoking, by measuring:

- Smoking satisfaction (satisfying, tastes good, and enjoys smoking).
- Psychological rewards (calms down, more awake, less irritable, helps concentrate, reduces hunger).
- Aversion (dizziness, nauseous).
- Enjoyment of respiratory tract sensations (single-item assessment).
- Craving reduction (single-item assessment).

7.7.2.4 Intention to Use THS 2.2 Questionnaire

Subjects in the THS 2.2 arm will complete themselves the questionnaire on their intention to use THS 2.2 using the ITUQ according to Appendix 1. The ITUQ comprises two sets of items:

- 1 item assessing intention to use THS 2.2 on a regular, ongoing basis to be rated on an ordinal scale with 6 timeframe categories. Only subjects who provide answer different from “definitely not” to this item will be asked to answer the next 6 items.

Confidentiality Statement

Data and information contained in this document are considered to constitute trade secrets and confidential commercial information, and the legal protections provided to such trade secrets and confidential information are hereby claimed under the provisions of applicable law. No part of this document may be publicly disclosed without the written consent of Philip Morris Products S.A.

- 6 items assessing several intentions to use THS 2.2 on a regular, ongoing basis to be rated on a 6-point scale ranging from “definitely not” to “definitely” with higher scores indicating greater likelihood to use THS 2.2.

Confidentiality Statement

Data and information contained in this document are considered to constitute trade secrets and confidential commercial information, and the legal protections provided to such trade secrets and confidential information are hereby claimed under the provisions of applicable law. No part of this document may be publicly disclosed without the written consent of Philip Morris Products S.A.

8 ADVERSE EVENTS

8.1 Definitions

8.1.1 Adverse Events

The FDA MRTP guideline [4] specifies this definition towards tobacco products, as follows: “An AE is any health-related event associated with the use of a tobacco product in humans, which is adverse or unfavorable, whether or not it is considered tobacco-product related”.

8.1.2 Serious Adverse Events

A serious adverse event (SAE) is defined as, but not limited to, any untoward medical occurrence that:

- Results in death.
- Is life-threatening.
- Requires inpatient hospitalization or prolongation of existing hospitalization.
- Results in persistent or significant disability/incapacity, or
- Is a congenital anomaly/birth defect.

Important medical events that may not result in death, be life-threatening, or require hospitalization may be considered an SAE when, based on appropriate medical judgment, they may jeopardize the subject or the subject may require medical or surgical intervention to prevent one of the outcomes listed in the above definitions.

Any pre-planned hospitalizations that are known at the time of signing the ICF will not be recorded as SAEs, however they will be recorded as AEs only. Any AE that occurs during this pre-planned hospitalization will be considered according to the above definitions.

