7.1 Informed Consent

The subject will be asked to provide his/her written consent to participate to the extension study (ICF for study participation) at the end of V10, after all the assessments of the original study are completed (section 1.3). The V10 assessments of the extension study can start only once the subject has signed the ICF.

In addition to the ICF for the extension study participation, only subjects who have previously provided consent for biobanking (and did not withdraw it) will be asked to provide his/her separate optional consent at V10 for the further collection of samples and storage for long-term biobanking at V16 (section 1.3.2):

- ICF for the additional biobanking of serum/plasma/urine samples for further measurements of BoExp and clinical risk endpoints.
- ICF for the additional biobanking of blood sample for further transcriptomics and lipidomics analysis/sample collection.

The subject's participation to the study does not depend on his/her consent for biobanking and will be separated from that for study participation. The additional consents will be captured in the CRF.

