7.3.1 Concomitant Disease, Previous and Ongoing Medications

A concomitant disease is defined as any clinically relevant medical condition that was either detected at V1, and/or was still ongoing at V1. Any untoward medical occurrence in a subject detected during the original and the extension studies, which was not present at V1 of the original study, must be documented as an AE. Worsening of a pre-existing condition from V1 onwards will also be documented as an AE.

All concomitant medication taken during the extension study (from enrolment at V10 to V16) will be documented in the source documents and recorded in the CRF of the extension study. Medication which is ongoing at V10 will be considered as a concomitant medication in the extension study. This applies to both prescription and over-the-counter products.

Records of medication taken include the drug name (preferably both generic and trade name), route of administration (*e.g.*, oral, intravenous), total daily dose/unit (*e.g.*, expressed in mg, mL, or IU), indication, the frequency, the start and (if applicable), the stop date (day, month and year). Any therapy changes (including changes of regimen) during the study are to be documented.

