### 12.7.4.1 Safety Reporting

All safety data collected during the study will be provided in listings by randomization arm, site, subject, and product use pattern category defined over the 12-month period. Safety study periods are defined as follows:

- Screening: [Screening to V3[
- Product Trial: [V3 to V4]
- Exposure: ]V4 to V16]
- Safety Follow-up: [Start to End of Safety Follow-up], where
  - the Start of Safety Follow-up is after Completion of V10 for subjects who complete the main study but do not enroll in the extension study, after Completion of V16 for completers of the extension study, or after the latter of the discontinuation date and the Early Termination visit date for non-completers

All summaries for safety parameters will be conducted on the Safety Population. Unless otherwise specified, summaries will be produced overall by randomization arm and product use pattern categories (see Section 4.1.2 “Definition of Product Use Pattern Categories”).

Safety data collected during the Product Trial period will be summarized by randomization arm in a separate table, including subjects in the Safety population who are not randomized.

AEs occurring during the safety follow-up will be summarized accounting for the number of subjects entered in the safety follow-up period.

Unless otherwise specified, safety data collected during the Screening period will be provided in listings only.

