#### **12.7.4.2.2 Serious Adverse Events (Including Deaths)**

Summary tables of SAEs will be presented using the same approach as for AEs by randomization arm (see Section “All Adverse Events”), and including the number of events and the number and percentage of subjects reporting at least one SAE broken down by seriousness criteria (fatal, life-threatening, requires hospitalization, results in disability/incapacity, congenital anomaly/birth defect) (Table 15.2.6.13). SAEs will also be summarized by product use pattern category, if there are at least 10 SAEs (Table 15.2.6.14).

SAEs will also be listed in separate listings by randomization arm and product use pattern category (Listing 15.3.6.2).

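### The SAE exemption for pre-planned hospitalizations is tied to an ICF signed after 26 weeks of randomized product use, so some on-product admissions can be recorded as AEs only

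*Protocol*

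**What the plan says.** Protocol 8.1.2 counts inpatient hospitalization as a seriousness criterion and then makes an exception: "Any pre-planned hospitalizations that are known at the time of signing the ICF will not be recorded as SAEs", with the qualification "however they will be recorded as AEs only". One safeguard follows: "Any AE that occurs during this pre-planned hospitalization will be considered according to the above definitions".

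Protocol 7.1 has the subject give "written consent to participate to the extension study (ICF for study participation) at the end of V10". Protocol 8.2.1 and 8.2.2 start AE collection for the extension at that same signature.

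Three other provisions bear on the point:
- Protocol 7.3.1 takes V1 as the reference for pre-existing disease. An untoward occurrence "which was not present at V1 of the original study, must be documented as an AE", and so must any worsening from V1 onwards.
- Protocol 8.2.1 requires an SAE form for any AE that meets a seriousness criterion.
- The SAP pools the two studies (12.1) and defines the safety period as "Exposure: ]V4 to V16" inclusive (12.7.4.1). Its SAE table is broken down by seriousness criterion, including hospitalization (12.7.4.2.2).

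**The concern.** An exemption for admissions planned before consent is sensible when consent precedes exposure, because it keeps out events that the product cannot have caused. Here consent to the extension comes halfway through exposure. The exemption therefore also reaches conditions that started or worsened on the randomized product.

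What is at stake is seriousness status. An admission classed as AE only does not enter the SAE tables and listing, and does not trigger the reports in Protocol 8.3: within 24 hours to the sponsor, and from the sponsor to FDA within 15 business days. Safety is a stated objective (objective 10), and the SAE summary is meant to cover all 12 months.

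**Working it through.** No figure in the plan is in dispute. The check compares reference dates and then follows cases through the rules.

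**Which ICF.** Section 8.1.2 does not say. Protocol 1.3.1, 7.1, 8.2.1 and 8.2.2, and the definition of screening failure, all use the term for the form signed at V10. Signature comes "at the end of V10, after all the assessments of the original study are completed".

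**Reference points in the two documents.**

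| Purpose | Reference | Source |
|---|---|---|
| Pre-existing condition versus AE | V1 | Protocol 7.3.1 |
| Comparison value for Grade 1 laboratory findings | V3 | Protocol 8.4.1 |
| Product-emergent AE | Enrollment, V3 of the main study | SAP 12.7.4.2, 4.1.1 |
| Start of randomized use | V4 | Protocol 6.3 |
| Safety exposure period | after V4, through V16 | SAP 12.7.4.1 |
| AE collection in the extension | ICF at V10 | Protocol 8.2.1, 8.2.2 |
| Pre-planned hospitalization exemption | ICF, read as V10 | Protocol 8.1.2 |

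**Timing.** SAP Table 17 puts Day 1 at study day 1 and V10 at study day 183, and Protocol 4.1 puts V16 at 364 days after V4.
- Exposure before the extension ICF: (183 − 1)/7 = 26.0 weeks.
- Share of the exposure period already elapsed: 182/364 = 50%.

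**Cases under the text as written.** In each, the admission takes place between V10 and V16.
1. Condition begins after V4; admission booked before V10. It is a product-emergent AE requiring hospitalization inside the safety period, but 8.1.2 makes it AE only.
2. Same condition; admission booked after V10. The exemption does not apply and the ordinary SAE criteria do.
3. Condition present and stable since V1; admission booked before V10. It is AE only, which is what such an exemption is for.

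Cases 1 and 2 differ only in the booking date, yet only one is an SAE. The safeguard in 8.1.2 does not help in case 1, because it concerns new AEs during the stay and not the condition that led to it. Protocol 8.2.2 carries AEs ongoing at V10 forward but says nothing about their seriousness. The SAE-form requirement in 8.2.1 points the other way from 8.1.2, and no text reconciles them.

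**Number affected.** The population at risk is about 0.65 × 950 = 617.5 subjects, taking the observed enrollment rate and the target size of the original study (Protocol 12.2, 5.1). The documents give no rate of hospitalization, SAEs or pending admissions. For scale only, an assumed 0.1% to 0.5% with case 1 would be 0.6 to 3.1 admissions. Nothing in the documents supports those rates, and the conclusion does not rest on them.

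**The case against.** The strongest reply is that no loss is demonstrated. The criterion in 8.1.2 is that an event requires hospitalization, not that the admission has happened, so a condition arising between V4 and V10 with an admission booked might already have been an SAE in the original study. Ongoing AEs are carried into the extension CRF (Protocol 11.1.1), and the safety management plan may settle the matter. This stands as a limit: neither the original protocol nor that plan is available. It does not cure the sentence, because nothing in these documents ensures the earlier classification. Reading the ICF as the V1 form would remove the problem, but the protocol's own usage is against it.

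A reader might also infer more than the documents support:
- *That the admissions vanish from the data.* They do not. They remain AEs, tabulated by arm, product use category, severity and relatedness.
- *That V1 is the reference everywhere else.* It is not, as the table shows; the extension uses several. The conflict is specifically with 7.3.1 and 8.2.1.
- *That only subjects who continue are affected.* This presumes that the original protocol has no similar sentence. Decliners also have only a 28-day follow-up, so a later admission of theirs would not be captured at all.
- *That lost events could hide SAEs through the table threshold.* The SAP says "SAEs will also be summarized by product use pattern category, if there are at least 10 SAEs". That condition governs one by-use table. The by-arm SAE table and the SAE listing have no such condition.
- *That the rule favours one arm.* It is worded identically for both, and no direction of bias is shown.

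Investigators may also exclude subjects at V10 on medical grounds (Protocol 5.1.2), which would reduce the number further. A pending admission is not itself an exclusion criterion.

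**Conclusion.** The point holds as a flaw in event classification. On its natural reading, 8.1.2 denies SAE status to an admission booked before V10 for a condition that began or worsened on product, when the stay itself falls after V10. Such an event is missing from SAE tables meant to span V4 to V16 and from expedited reporting. That sits in tension with the V1 reference in 7.3.1 and the SAE-form requirement in 8.2.1.

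The size is unknown and probably small: the study recruited healthy adult smokers, and the booking and the stay must fall on opposite sides of V10. The conclusion assumes that the ICF in 8.1.2 is the extension ICF and that sites follow the sentence literally. If sites read it differently from one another, identical events would be classified inconsistently, which also calls for a clarification. It is worth correcting because the change is cheap, not because a material distortion of the safety results has been shown.

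**What to change.** In Protocol 8.1.2, or in the safety management plan:
- Limit the exemption to pre-planned hospitalizations for a condition that was present at V1 of the original study and has not worsened since, whenever the admission was planned. This also settles the stable V1 condition whose admission was booked between V1 and V10.
- State that an admission for a condition that began or worsened after V1 is judged under the ordinary SAE criteria, even if it was planned before V10.

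For data already collected, review before database lock all extension AEs that involved a hospitalization but have no SAE form, and reclassify those with onset or worsening after V1. The search should start from hospitalization and not from a pre-planned code, because Protocol 8.2.1 lists no such item among the recorded AE fields. If the database is already locked, disclose any such events in the CSR.

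The cost is a short text change, a limited set of queries, a slightly higher SAE count, and a few late SAE forms with the onward reports that Protocol 8.3 requires.
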